7.6 Data Management

All data collected for the study should be recorded accurately, promptly, and legibly. For primary data collection, the investigator or qualified designee is responsible for recording and verifying the accuracy of subject data. For data *not* obtained from a primary source (i.e., secondary data, such as claims and electronic health records), the investigator is responsible for reviewing data quality and relevance to the best of the investigator's knowledge. The investigator confirms that the quality and relevance of data has been assessed to meet the minimum requirements for all study objectives.

If this study has been outsourced, the institutional policies of the supplier should be followed for development of data management plans. However, the supplier should ensure compliance with Good Pharmacoepidemiology Practice, and all applicable federal, state, and local laws, rules and regulations relating to the conduct of the study.

Data Management Software and Hardware:

Data management and analyses will be performed using SAS 9.4.

Description of Data Preparation and Methods for Data Retrieval and Collection:

This surveillance will utilize post-marketing database studies that must comply with the quality standards stipulated in the ministerial ordinance for good post-marketing study practices (GPSP) and their related guidelines.

| | |
|--|--|
| PRODUCT: MK-1986 | PROTOCOL/AMENDMENT VERSION NO.: 1986-047-00-V3 |
| REVOPS ID NO: NIS106696 EPIDEMILOGY NO.(PE STUDIES ONLY): EP08063.004 | NIR DRC APPROVAL DATE: NOVEMBER 25, 2025 |

Data management for this surveillance will be conducted using standard MID-NET processes. The processes will take into consideration any data governance imposed on the data source. MSD and CCI will adhere to all local and regional laws on data protection and privacy.

7.7 Programming Quality

This study will incorporate the following quality checks for data analysis and reporting programming:

- Creating a program requirements and specification document (PRS)
- Developing and testing of statistical programs which includes ensuring the programs run successfully and all output are reviewed to ensure they meet the criteria included in the (PRS). This includes validating that all inputs (metadata or parameter values) are correctly specified in the programs and are consistent with the PRS.
- Independent Review and Testing, conducted by a second programmer to ensure that the input and outputs of the programs created by the first programmer meet the documented PRS. This includes the following 2 activities:
 - Review of code to ensure the program aligns with the PRS
 - Execution of code and review of results for some or all scenarios

And may include the following activity:

- Parallel programming of a small piece of critical code
- Independent Double Programming, conducted by second programmer. After programming is completed, the programs and results of the second programmer are compared to those of first programmer to ensure consistency. If discrepancies are found, the programmers will repeat steps until consistency is achieved.
- Review of outputs/results to ensure accuracy and format of each deliverable.

7.8 Data Analysis

7.8.1 Patient characteristics

Basic statistics on the surveillance populations will be presented as n (%), mean \pm SD, or median (interquartile range [IQR]), as appropriate.

| | |
|--|--|
| PRODUCT: MK-1986 | PROTOCOL/AMENDMENT VERSION NO.: 1986-047-00-V3 |
| REVOPS ID NO: NIS106696 EPIDEMILOGY NO.(PE STUDIES ONLY): EP08063.004 | NIR DRC APPROVAL DATE: NOVEMBER 25, 2025 |

7.8.2 Primary objective

Incidence rates of peripheral neuropathy and optic nerve disorder and binomial confidence intervals will be calculated descriptively for tedizolid and linezolid groups separately. The number and percentage of patients with peripheral neuropathy and optic nerve disorder will be calculated. For all patients, the exposure time starts the day after the initiation of treatment date.

If there are 10 or more events observed for each treatment group, crude odds ratios and 95% CI will be estimated to be using logistic regression models, to compare the risk of peripheral neuropathy and optic nerve disorder between the tedizolid group and linezolid group (16).

Inverse probability of treatment weighting (IPTW) approach will be used to adjust for potential confounding between the tedizolid and linezolid groups (17,18). PS will be generated using probability estimates from a logistic regression model in which treatment with tedizolid or linezolid will be the binary dependent variable and patient characteristics (see Section 7.3.3) will be used as predictors of being treated with tedizolid or linezolid, if 10 patients exposed to tedizolid are observed per predictor. The IPTW approach uses weights derived from the PS to create a pseudo-population such that the distribution of baseline covariates in the population is independent of treatment assignment. For each patient, the weight will be assigned as the inverse of the propensity score for the tedizolid group and as the inverse of 1 minus the propensity score for the linezolid group will be calculated. The balance of baseline covariates will be assessed by using standardized mean differences; covariates will be well-balanced if the standardized mean difference is <0.1 (19,20). The distribution and variance for continuous variables will also be assessed between the treatment groups (20). Once balance of the covariates is achieved across the two treatment groups, the average difference in the risk of peripheral neuropathy and optic nerve disorder between the two treatment groups will be estimated using logistic regression models accounting for variance estimation (e.g., robust variance estimator) (21).

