7 RESEARCH METHODS

7.1 Study Design

This is an observational cohort study with active comparator new user design, using MID-NET. The study will be conducted using only structured secondary data. Patients with recorded diagnosis of MRSA and one of the common indications between tedizolid and linezolid (1: Deep Skin Infections, Chronic Abscesses, 2: Secondary infection of trauma, burns, and surgical wounds) (see Appendix A) followed by a prescription of tedizolid or linezolid, after the marketing of tedizolid on 21-Aug-2018, will be included in the study (3-5). Incidence rates of diagnosed peripheral neuropathy and optic nerve disorder and binomial confidence intervals will be calculated descriptively for tedizolid and linezolid groups separately. If sample size is sufficient (10 or more events observed for each treatment group), the odds of diagnosed peripheral neuropathy and optic nerve disorder between those taking tedizolid and those taking linezolid will be compared, and the odds ratio will be estimated. Active comparator new user designs are useful for mitigating bias in observational studies, given all other design features are reasonable (6).

In this study, a new user design will be adopted for the following reasons.

- By including only cases without prior use of tedizolid or linezolid, the impact of selection bias and confounding can be reduced in this study using secondary data.
- If cases with a history of tedizolid or linezolid use are included in this study, the study population may consist of individuals for whom tedizolid or linezolid was previously discontinued due to adverse reactions attributable to tedizolid or linezolid, and then re-prescribed. In such a population, the risk of outcomes attributable to tedizolid or linezolid is relatively higher compared with other populations.

In addition, sensitivity analysis will be conducted in which cases with prescriptions of anti-MRSA drugs other than tedizolid or linezolid prior to the prescription of tedizolid or linezolid are excluded. (see Section 7.8.3 (1))

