7.5 Study Size

The incidence of adverse events related to peripheral neuropathy and optic nerve disorder in the international Phase III clinical trials (Studies TR701-112 and 113) was 1.2% (8/662 patients) and 0.3% (2/662 patients), respectively. Based on this consideration, the incidence of an event in the tedizolid was assumed to be 0.3% to 1.2%.

[figure not shown]
Based on the results of the feasibility study, the median continued prescription period for tedizolid was **CCI** days, with a 75% tile of **CCI** days. From the above, a follow-up period of about 30 days was assumed.

According to the results of the MID-NET survey, there were **CCI** cases of patients prescribed tedizolid with confirmed diagnosis of MRSA during the period from May 2018 to March 2025. Considering the loss of cases due to exclusion criteria, it is estimated 100-200 patients will be included in the study.

Under this assumption, the power is shown below (Fig. 3) when the risk ratio (rate ratio) is set between 1.2 and 5.0 and the sample size of the tedizolid group is varied in 20 increments from 100 to 200 of the predicted accumulation. Note that sample size of the control group (linezolid) was assumed to be approximately 10 times that of the tedizolid group. A generalized linear model assuming Poisson distribution was used to detect group differences.

Figure 3: Power at each sample size assuming an event incidence rate of 1.2% and a risk ratio of 1.2-5 in the tedizolid group

| | |
|---|--|
| PRODUCT: MK-1986 | PROTOCOL/AMENDMENT VERSION NO.: 1986-047-00-V3 |
| REVOPS ID NO: NIS106696 EPIDEMIOLOGY NO.(PE STUDIES ONLY): EP08063.004 | NIR DRC APPROVAL DATE: NOVEMBER 25, 2025 |

For each condition, there was no sample size required for Power to be greater than 80%.

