7.10 Limitations of the Research Methods

The number of patients treated with tedizolid or linezolid are likely to be very small because of the low use of these medications, even before applying the inclusion and exclusion criteria (which requires a MRSA diagnosis and specific prior therapies). In addition, the treatment period for these cohorts will be relatively short. Given very small numbers (patients / patient years), a high-risk population, previous treatment with other MRSA drugs that could be

| | |
|---|--|
| PRODUCT: MK-1986 | PROTOCOL/AMENDMENT VERSION NO.: 1986-047-00-V3 |
| REVOPS ID NO: NIS106696 EPIDEMIOLOGY NO.(PE STUDIES ONLY): EP08063.004 | NIR DRC APPROVAL DATE: NOVEMBER 25, 2025 |

associated with peripheral neuropathy and optic nerve disorder that are diagnosed at a later time, and many concomitant medications that can also be associated with the peripheral neuropathy and optic nerve disorder, it is possible that rates may be higher than observed in clinical trials or that there will appear to be imbalances between the two cohorts (who are actually taking bioequivalent medications), etc. Therefore, assessment of OR is likely to be inconclusive and care must be taken in interpretation of the data and generalizability of the surveillance results. Also, if there are no events in either the tedizolid or linezolid group, the OR cannot be calculated. Crude OR should not be calculated with less than 10 events.

When estimating the marginal effect of rare exposure, results using PS methods could be biased (22). Logistic regression models generating PS with small number of patients in tedizolid group might suffer from convergence problems and unstable parameter/coefficients estimates, as limited data provide insufficient information for reliable model fitting (23). Additionally, when a treatment group is rare, this group of patients are likely to receive very large weights, and thus have a disproportionate influence on the analysis, which is suspected to be the case with tedizolid based on the feasibility assessment. As these patients represent only a small proportion of the target study population, their disproportionate influence on the analysis may affect the precision of the average marginal effect estimate (24).

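### At the protocol's own sample size and incidence, the rule of 10 events in each group means the crude odds ratio for the primary objective will almost certainly never be calculated

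*Protocol*

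**What the plan says.** The only objective (Protocol 6.2.1) is to compare the risk of the two outcomes between tedizolid and linezolid users. Three sections restrict that comparison by event count:

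- Section 7.8.2: "If there are 10 or more events observed for each treatment group, crude odds ratios and 95% CI will be estimated".
- Section 7.1: "If sample size is sufficient (10 or more events observed for each treatment group"), and only then are the odds compared and an odds ratio estimated.
- Section 7.10: "Crude OR should not be calculated with less than 10 events". It does not say whether the count is per group or in total.

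Section 7.5 gives the planning figures. Incidence in the phase III trials "was 1.2% (8/662 patients) and 0.3% (2/662 patients), respectively", for peripheral neuropathy and optic nerve disorder in that order, and on that basis "the incidence of an event in the tedizolid was assumed to be 0.3% to 1.2" percent. For tedizolid, "it is estimated 100-200 patients will be included in the study". The "sample size of the control group (linezolid) was assumed to be approximately 10 times that of the tedizolid group", and "the risk ratio (rate ratio) is set between 1.2 and 5.0". Power comes from a Poisson model, and the section concludes that no condition exceeds 80%.

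Whatever the event count, Section 7.8.2 also reports the number, percentage and incidence with a binomial interval for each group. Its propensity-score paragraph has a different condition: 10 tedizolid patients per predictor.

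**The concern.** The event condition and the planning figures sit in the same protocol but do not fit together. If only one or two tedizolid events are expected, a requirement of ten removes the comparison almost by design, and the protocol names no comparative summary to take its place. The reader would get two separate intervals and would have to form the contrast unaided.

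Three further matters follow. Data that say something useful about relative risk would go unreported, whether alarming or reassuring. The power statement describes a procedure that the plan would almost never carry out. And the condition is worded differently in different sections, so it is unclear whether the weighted odds ratio is subject to it.

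**Working it through.** **Inputs.** Tedizolid n = 100 to 200, linezolid 10n, tedizolid incidence 0.3% or 1.2%, risk ratio up to 5.0 (all Section 7.5); at least 10 events in each group (7.1, 7.8.2). The significance level for Figure 3 is not stated; two-sided 0.05 is assumed.

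**The plan's own power statement.** The caption of Figure 3 puts the 1.2% in the tedizolid group, so linezolid risk is 1.2%/RR. The most favourable case is n = 200, RR = 5:

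- Expected events: 200 × 0.012 = 2.4, and 2,000 × 0.012/5 = 4.8.
- SE of the log rate ratio = √(1/2.4 + 1/4.8) = 0.791.
- z = ln 5/0.791 = 2.04, so Wald power = Φ(2.04 − 1.96) ≈ 0.53.

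That is below 0.80, so the statement in 7.5 reproduces, but for a test with no event condition. In the same case an exact conditional Poisson test has power of about 0.33. Requiring 10 events in each group as well reduces that to about 0.000005.

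**Chance that the tedizolid group reaches 10 events.** P(X ≥ 10) with X ~ Binomial(n, p):

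| n | p | expected events | P(X ≥ 10) |
|---|---|---|---|
| 100 | 0.3% | 0.3 | 8 × 10⁻¹³ |
| 200 | 0.3% | 0.6 | 8 × 10⁻¹⁰ |
| 100 | 1.2% | 1.2 | 4 × 10⁻⁷ |
| 200 | 1.2% | 2.4 | 0.00018 |

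These are upper bounds for the full condition, since linezolid must reach 10 as well. Pooling the two outcomes (1.5%, n = 200) gives only about 0.001.

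**What would be needed.** Solving P(X ≥ 10) = 0.5 gives a tedizolid risk of 9.6% at n = 100 or 4.8% at n = 200, that is 8 or 4 times the top of the assumed range. At a fixed 1.2%, about 806 tedizolid patients would be needed. At n = 200, ten events mean an observed risk of 10/200 = 5%.

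**Contrasts that would be withheld** (200 against 2,000 patients, exact conditional 95% intervals):

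- 9 against 9 events: OR 10.4 (3.6 to 30.0).
- 9 against 24: OR 3.9 (1.6 to 8.8).
- 2 against 24, about what equal risks of 1.2% would give: OR 0.83 (0.09 to 3.4), which excludes a fourfold increase.

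**Scope of the condition.** Section 7.1 applies it to the comparison as a whole. In 7.8.2 it is attached to the crude odds ratio, and the weighting paragraph requires only 10 tedizolid patients per predictor. Table 4 has nine covariates, so 9 × 10 = 90 patients suffice, which is met at 100 to 200. Read literally, 7.8.2 would allow the weighted model with 0 to 2 tedizolid events while withholding the simpler crude estimate.

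**The case against.** The best defence is that the authors know the study is small and say so. It is called exploratory, the ENCePP checklist marks hypothesis testing as not applicable, 7.5 concedes that power never exceeds 80%, and 7.10 warns that the odds ratio is likely to be inconclusive. Declining to publish unadjusted odds ratios on a handful of events, with unvalidated outcome definitions and acknowledged confounding, is a defensible choice. Small counts are fragile: 4/200 against 8/2,000 gives p = 0.018, but one tedizolid event fewer gives p = 0.07. The amendment log also shows that the wording in 7.1 was added after the consultation with PMDA, so it was deliberate.

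Much of this stands, but it does not close the gap. An odds ratio expected to be inconclusive is not the same as one that will almost never be calculated, and the protocol states only the former. Nor does 7.10's remark that rates may exceed those in trials rescue the rule: at 3.6%, three times the upper assumption, the tedizolid group reaches ten events with probability 0.19 at n = 200 and 0.003 at n = 100.

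Three stronger readings are tempting and are not supported:

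- That no comparison at all is possible. On the literal wording of 7.8.2 the weighted estimate is not subject to the event count; the near-impossibility applies to the crude odds ratio, and to the whole comparison only under 7.1.
- That any odds ratio reported must be unfavourable to tedizolid. The rule selects on a high absolute tedizolid count, not on a high ratio: 10/200 against 100/2,000 satisfies it with OR 1.0 (0.46 to 1.96).
- That the objective is left without data. Incidences with intervals are always reported for each group; what is lost is the contrast.

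**Conclusion.** The point holds for the crude odds ratio. With 100 to 200 tedizolid patients and 0.3% to 1.2% incidence, the event condition is met with probability of at most about 0.0002 for either outcome, so the contrast that serves the sole primary objective will almost certainly be missing from the report. Figure 3 (at most about 53% by Wald test, assuming two-sided 0.05) does not describe the plan as written. Sections 7.1 and 7.8.2 need reconciling on the weighted estimate.

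The probability rests on the incidence in 7.5 carrying over to MID-NET. If the true tedizolid risk were about 5% or more, the rule would be met often at n = 200 (0.77 at 6%), though still rarely at n = 100 (0.08 at 6%).

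**What to change.** 1. Sections 7.1, 7.8.2 and 7.10, and the abstract: remove the event condition for the crude contrast. At any event count report an exact (or mid-P) odds ratio and a risk difference, each with a 95% interval and labelled unadjusted and exploratory. With zero events in one group the exact odds ratio still gives a one-sided limit.
2. Reconcile 7.1 and 7.8.2 so that a minimum-event rule applies explicitly to the weighted model, and say whether it counts events per group and per outcome.
3. Section 7.5: state that Figure 3 is for a test without an event condition, give the chance of reaching 10 tedizolid events, and add the expected precision. With zero events the exact 95% upper limit is 1 − 0.025^(1/n): 3.6% at n = 100 and 1.8% at n = 200.

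The analysis cost is small: a few lines of standard exact procedures in SAS. The real costs are wide unadjusted intervals that need careful wording, and a protocol update that probably has to be agreed with PMDA, which approved the protocol on December 9, 2025, with data collection planned to start on January 16, 2026.

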7.8.3 Sensitivity analyses

The following sensitivity analyses are planned:

- 1) The analysis will be conducted that does not allow for a history of administration of anti-MRSA drugs other than tedizolid and linezolid within lookback period.
- 2) The analysis will be conducted with the lookback period changed to 30 days.
- 3) The analysis will be conducted with the gap period changed to 7 days.
- 4) The analysis will be conducted with the following changes to the inclusion criteria 2.

Patients with confirmed or suspected diagnosis of MRSA (ICD-10: A49.0 and disease name notation: MRSA infection) and confirmed diagnosis of indications for both tedizolid and linezolid (1: Deep Skin Infections, Chronic Abscesses, 2: Secondary infection of trauma, burns, and surgical wounds) in the same month or

| | |
|---|--|
| PRODUCT: MK-1986 | PROTOCOL/AMENDMENT VERSION NO.: 1986-047-00-V3 |
| REVOPS ID NO: NIS106696 EPIDEMIOLOGY NO.(PE STUDIES ONLY): EP08063.004 | NIR DRC APPROVAL DATE: NOVEMBER 25, 2025 |

previous month of the index date. The disease code list is provided as Appendix A.

- 5) The analysis will be conducted with the following changes to the inclusion criteria 2. Patients with confirmed or suspected / probable diagnosis of MRSA (ICD-10: A49.0 and disease name notation: MRSA infection, Staphylococcal infection, MRCNS jinfection, MSSA infection, MRSE infection, and Vancomycin-resistant Staphylococcus aureus infection) and confirmed diagnosis of indications for both tedizolid and linezolid (1: Deep Skin Infections, Chronic Abscesses, 2: Secondary infection of trauma, burns, and surgical wounds) in the same month or previous month of the index date. The disease code list is provided as Appendix A.
- 6) The analysis will be conducted with the following changes to the exclusion criteria 3. Patients who have one or more histories of peripheral neuropathy and optic nerve disorder (see Section 7.3.2 for details) within 365 days prior to the index date.
- 7) The analysis will be conducted with the following changes to the outcome definition. Peripheral neuropathy is defined as cases meeting all of the following three conditions:
 1. A confirmed diagnosis of peripheral neuropathy (ICD-10 code).
 2. In the same month as, the month prior to, or the month after the confirmed diagnosis of peripheral neuropathy, either a treatment drug for peripheral neuropathy or pain was prescribed, or blood purification therapy for immune-mediated neuropathy was performed.
 3. In the same month as, the month prior to, or the month after the confirmed diagnosis of peripheral neuropathy, a test related to peripheral neuropathy was performed.
Optic nerve disorder is defined as cases meeting all of the following three conditions:
 1. A confirmed diagnosis of optic nerve disorder (ICD-10 code).
 2. In the same month as, the month prior to, or the month after the confirmed diagnosis of optic nerve disorder, vitamin B12 or corticosteroids were prescribed.
 3. In the same month as, the month prior to, or the month after the confirmed diagnosis, any of the relevant tests for optic nerve disorder (general, outpatient, or imaging tests) were performed.
The first event that meets any of the above definitions will be used for the analysis. The outcome occurrence date will be the earliest of the following: for peripheral neuropathy, the prescription date of treatment drugs, the implementation date of blood purification therapy, or the test date; for optic nerve disorder, the prescription date of treatment drugs or the test date.

| | |
|---|--|
| PRODUCT: MK-1986 | PROTOCOL/AMENDMENT VERSION NO.: 1986-047-00-V3 |
| REVOPS ID NO: NIS106696 EPIDEMIOLOGY NO.(PE STUDIES ONLY): EP08063.004 | NIR DRC APPROVAL DATE: NOVEMBER 25, 2025 |

8) The analysis will be conducted with the following changes to the outcome definition.

Peripheral neuropathy is defined as cases meeting the following condition:

1. A confirmed diagnosis of peripheral neuropathy (ICD-10 code).

Optic nerve disorder is defined as cases meeting the following condition:

1. A confirmed diagnosis of optic nerve disorder (ICD-10 code).

The first event that meets any of the above definitions will be used for the analysis. The outcome occurrence date will be set as the last day of the month of the confirmed diagnosis.

